13.3 Subgroup Analyses

Subgroup analyses of primary efficacy endpoint include the following pre-study characteristic variables. The subgroup analyses will be based on the ITT population and use observed data only.

- Site
- Age: <65 years versus ≥65 years
- Sex
- Prior hypotensive medication experience category 1: Combination Therapy, Prostaglandin (monotherapy), Other (monotherapy), No Prior Therapy
- Prior hypotensive medication experience category 2: Prior Prostaglandin, No Prior Prostaglandin
- Maximum baseline IOP value: <17 mmHg, <19 mmHg, <21 mmHg, <23 mmHg, <25 mmHg, <27 mmHg, <30 mmHg, <32 mmHg

For all subgroup analyses, except maximum baseline IOP value, mean diurnal IOP at Week 4 will be compared between treatment groups (using an ANCOVA model with treatment and subgroup as the main effects, mean diurnal baseline IOP as a covariate, and the interaction of treatment and subgroup). The LS mean differences (netarsudil – placebo), p-values for testing the treatment difference, and the interaction of treatment by subgroup will be presented.

Sites with fewer than five subjects will be pooled together for the analysis..

The primary efficacy analysis of mean diurnal IOP at Week 4 will be completed for maximum baseline IOP <17 mmHg, <19 mmHg, <21 mmHg, <23 mmHg, <25 mmHg, <27 mmHg, <30 mmHg, <32 mmHg, and <35 mmHg

The secondary efficacy analysis of two-sample t-test for mean and mean change from baseline in IOP at each timeline and for diurnal mean will be completed for maximum baseline IOP <17 mmHg, <19 mmHg, <21 mmHg, <23 mmHg, <25 mmHg, <27 mmHg, <30 mmHg, <32 mmHg, and <35 mmHg.

Additional post-hoc analyses were performed for IOP of subjects with prior hypotensive therapy and subjects with no prior therapy.

14. Exploratory Analyses

There are no exploratory analyses planned for this study.

15. Safety Analyses – Treatment Period

All safety analyses will be conducted using the safety population.

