4. STUDY POPULATION SELECTION

4.1 Study Population

A total of approximately 208 Japanese subjects will be enrolled in this study at approximately 30 investigational sites in Japan comprising a total of 52 subjects per treatment arm for each of the 4 treatment arms. Subjects will be at least 20 years of age with diagnosed OAG or OHT, each of whom meets all inclusion criteria and none of the exclusion criteria.

Planned enrollment numbers are higher (208 total, 52 subjects per arm) than statistically required for demonstrating efficacy (approximately 49 intent-to-treat [ITT] subjects per arm for 90% power) to account for the potential for subjects who do not complete the entire dosing period, or who have disqualifications. Over-enrollment (beyond 208 subjects) is to be undertaken only after communication between the investigational site and the Sponsor representative.

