4.2 Masking

Treatment assignments will be masked to the Investigator, the clinical study team (Sponsor, personnel involved in day to day study management, Monitors, Data Managers, and Statisticians), and the subjects for the duration of the study. Only in case of medical emergency or occurrence of AEs that warrant unmasking in the opinion of the Investigator, will the treatment assignment(s) be unmasked and made available to the Investigator and the Sponsor Medical Monitor or designee. Individual unmasking by the Investigator will normally result in withdrawal of the subject from the study and should only be performed for the specific subject requiring unmasking. In the absence of medical need, the randomization code will not be available to the above personnel until after the study is completed and the database is unlocked.

5. Sample Size and Power Considerations

Assuming a two-sided test with alpha = 0.05, a common standard deviation (SD) of 3.5 mmHg at each time point yielding a common SD of 3.0 for the diurnal mean, and a correlation among time points of 0.60, 49 intent-to-treat (ITT) subjects per arm yields at least 90% power to demonstrate superiority of netarsudil (0.01%, 0.02%, or 0.04%) to placebo in mean diurnal study eye IOP (average of 09:00, 11:00, and 16:00 hours) at the Week 4 visit assuming a difference of at least 2.0 mmHg in the mean diurnal IOP. Accounting for approximately a 5% discontinuation rate, 52 subjects per arm (208 total) will be enrolled.

6. Data Preparation

Study data will be recorded via electronic case report forms (eCRF). Each authorized study staff member will receive a unique access account in order to use the Electronic Data Capture (EDC) system. Access accounts will not be shared among study staff. Authorized users will make entries and/or changes to the eCRFs via a secure internet access. Each completed set of eCRFs will be reviewed by the Investigator

who will then electronically sign and date the eCRF confirming that data for the subjects are complete and accurate.

Final analyses outlined in this document will be carried out after the following have occurred:

- All data management requirements are met according to [REDACTED] standard operating procedures, including data entry, performance of edit and validation checks, documentation and resolution of data queries, and database lock with written authorization provided by appropriate [REDACTED] and Sponsor personnel.

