14.2.5.1	Categorical Summary in Study Eye Mean Diurnal Intraocular Pressure (mmHg) by Visit - Observed Data	Intent-to-Treat Population
14.2.5.2	Categorical Summary in Study Eye Mean Diurnal Intraocular Pressure (mmHg) by Visit - Observed Data	Per Protocol Population
14.2.6.1	ANCOVA for Study Eye Mean Diurnal IOP at Week 4 by Subgroup of Site - Observed Data	Intent-to-Treat Population
14.2.6.2	ANCOVA for Study Eye Mean Diurnal IOP at Week 4 by Subgroup of Age Category (<65 Years vs ≥65 Years) - Observed Data	Intent-to-Treat Population
14.2.6.3	ANCOVA for Study Eye Mean Diurnal IOP at Week 4 by Subgroup of Sex - Observed Data	Intent-to-Treat Population

14.2.6.4	ANCOVA for Study Eye Mean Diurnal IOP at Week 4 by Subgroup of Prior Hypotensive Medication Category 1 - Observed Data	Intent-to-Treat Population
14.2.6.5	ANCOVA for Study Eye Mean Diurnal IOP at Week 4 Prior Hypotensive Medication Category 2 - Observed Data	Intent-to-Treat Population
14.3.1.1	Overall Summary of Treatment-Emergent Adverse Events by Treatment Group	Safety Population
14.3.1.2	Number and Percentage of Subjects with Ocular Treatment-Emergent Adverse Events by Treatment Group, System Organ Class, and Preferred Term	Safety Population
14.3.1.3	Number and Percentage of Subjects with Non-Ocular Treatment-Emergent Adverse Events by Treatment Group, System Organ Class, and Preferred Term	Safety Population
14.3.1.4	Number and Percentage of Subjects with Serious Treatment-Emergent Adverse Events by Treatment Group, System Organ Class, and Preferred Term	Safety Population
14.3.1.5	Number and Percentage of Subjects with Treatment-Related Treatment-Emergent Adverse Events by Treatment Group, System Organ Class, and Preferred Term	Safety Population
14.3.1.6	Number and Percentage of Subjects with Treatment-Emergent Adverse Events by Maximum Severity, Treatment Group, System Organ Class, and Preferred Term	Safety Population
14.3.2.1	Mean and Mean Change from Baseline in Study Eye Best Corrected Visual Acuity Scores by Treatment Group and Visit	Safety Population
14.3.2.2	Mean and Mean Change from Baseline in Fellow Eye Best Corrected Visual Acuity Scores by Treatment Group and Visit	Safety Population
14.3.3.1	Summary of Study Eye Biomicroscopy Results by Treatment Group and Visit	Safety Population
14.3.3.2	Summary of Fellow Eye Biomicroscopy Results by Treatment Group and Visit	Safety Population

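### The site subgroup model in SAP 13.3 pools on total site size with no per-arm minimum, so its site-averaged treatment differences may not be estimable and its site-level differences are too imprecise to read

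*SAP*

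**What the plan says.** SAP 13.3 lists site first among the subgroups for the primary endpoint. Apart from maximum baseline IOP, every subgroup gets the same model: an "ANCOVA model with treatment and subgroup as the main effects, mean diurnal baseline IOP as a covariate, and the interaction of treatment and subgroup". It is fitted to ITT subjects with observed data only. The promised output is LS mean differences between netarsudil and placebo, p-values for the treatment difference, and the interaction. For site, one further rule applies: "Sites with fewer than five subjects will be pooled together for the analysis".

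The list of tables in SAP Section 21 gives the output as Table 14.2.6.1, "ANCOVA for Study Eye Mean Diurnal IOP at Week 4 by Subgroup of Site - Observed Data".

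Protocol 4.1 plans about 208 subjects, 52 per arm, at "approximately 30 investigational sites in Japan". SAP 4.1 randomizes 1:1:1:1, stratified by site. Neither document states a block size, a rule for empty treatment-by-site cells, or whether the site table reports differences within each site or one difference averaged over sites.

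**The concern.** The pooling rule counts subjects across four arms, whereas the interaction model needs subjects in every arm of every site level. A site of five escapes pooling with an average of 1.25 subjects per arm, and because nothing is imputed, one missing Week 4 value can empty a cell.

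Table 14.2.6.1 is the only listed table that examines site, and the primary ANCOVA has no site term. If the table prints non-estimable results, or site differences that swing widely by chance, the trial has no usable look at whether the effect is consistent across sites.

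**Working it through.** **Inputs from the documents.** 208 subjects, about 30 sites, four arms (Protocol 4.1); 5% discontinuation, SD 3.0 mmHg for the diurnal mean and a 2.0 mmHg difference (SAP Section 5).

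**Assumptions.** 5% of subjects missing at Week 4; blocks of 4, blocks of 8 or no blocking; site sizes from even to strongly uneven; residual SD after baseline adjustment of 2.0–3.0 mmHg.

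**The plan's own figure.** SAP Section 5 states "49 intent-to-treat (ITT) subjects per arm yields at least 90% power", "assuming a difference of at least 2.0 mmHg in the mean diurnal IOP".
- SD of the diurnal mean = 3.5 × √((1 + 2 × 0.60)/3) = 2.997, which agrees with the stated 3.0.
- n = 2 × (1.960 + 1.282)² × 3.0²/2.0² = 47.3, so 48 by the normal approximation. The noncentral t gives 89.8% power at 48 and 90.4% at 49.
- 49/0.95 = 51.6, so 52 per arm.

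The sample size reproduces.

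**Cell size.** 208/30 = 6.93 per site; 6.93/4 = 1.73 per arm per site; × 0.95 = 1.65 observed. This is an average. With even sites and blocks of 4, 98% of cells hold one or two observed subjects. With uneven sites 58–77% do, and 22–41% hold three or more.

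**Problem 1: the difference averaged over sites.** It needs at least one observed subject in the active arm and in placebo at every site level. A hand check for even recruitment and blocks of 4 uses 28 sites of 7 and 2 of 6 (28 × 7 + 2 × 6 = 208). An arm with one subject is empty with probability 0.05, an arm with two with probability 0.05² = 0.0025.
- Site of 7 (arms 2, 2, 2, 1): the given pair includes the single-subject arm half the time. Failure = ½ × (1 − 0.95 × 0.9975) + ½ × (1 − 0.9975²) = 0.0287.
- Site of 6 (arms 2, 2, 1, 1): failure = (1/6)(1 − 0.95²) + (4/6)(1 − 0.95 × 0.9975) + (1/6)(1 − 0.9975²) = 0.0520.
- Non-estimable for a given concentration = 1 − (1 − 0.0287)²⁸ × (1 − 0.0520)² = 60%.

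Simulation over the wider assumptions, with 5% missing, per concentration:

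| Site sizes | Blocks of 4 | Blocks of 8 | No blocking |
|---|---|---|---|
| Even | 63% | 64% | 100% |
| Mildly uneven | 46% | 78% | >99% |
| Moderately uneven | 35% | 71% | 99% |
| Strongly uneven | 28% | 62% | 98% |

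A repeat simulation gave 28–60% for blocks of 4 and 58–71% for blocks of 8, so the combined ranges are 28–63% and 58–78%. With blocks of 4 and nothing missing the figure is near 0%, because any site of five or more has completed a block.

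**Problem 2: differences within a site.** Under blocking these are non-estimable in only about 2–6% of cases (20–30% without blocking). Their precision is SE = SD × √(2/m) with m subjects per cell, and the chance of pointing towards placebo when the true effect is 2.0 mmHg is 1 − Φ(2.0/SE):

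| Residual SD | m | SE (mmHg) | Favours placebo |
|---|---|---|---|
| 2.0 | 2 | 2.00 | 16% |
| 2.0 | 1.5 | 2.31 | 19% |
| 3.0 | 2 | 3.00 | 25% |
| 3.0 | 1.5 | 3.46 | 28% |

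**Interaction test.** About 18–30 site levels remain after pooling. With three degrees of freedom per level beyond the first, the test has 3 × 17 = 51 to 3 × 29 = 87 numerator degrees of freedom.

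**The case against.** This is one supportive, observed-data table in a Phase 2 trial. Protocol 9.6.2 makes subgroup analyses optional, and no success rule or sample size depends on the table. The estimability figures rest on a block size and a missingness rate that the plan does not fix. All of this stands, and it is why the point is minor.

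A reader might also infer stronger things that the documents do not support:
- **Any empty cell removes every contrast.** It does not. An empty cell in one netarsudil arm removes only that concentration's site-averaged difference; only an empty placebo cell removes all three.
- **The output is often non-estimable and otherwise noise.** This joins two different quantities. Non-estimability is the risk for the site-averaged difference, and imprecision is the problem for the site-level ones. When estimable, the site-averaged difference is not noise: with 30 sites of 7 in blocks of 4, none missing, and SD 3.0, the mean of 1/n(active) + 1/n(placebo) is 2 × (0.75 × 0.5 + 0.25 × 1) = 1.25, so SE = 3.0 × √(1.25/30) = 0.61 mmHg. The planned primary comparison has 3.0 × √(2/49) = 0.61 mmHg.
- **The sign of a site difference is largely chance.** If 16–28% favour placebo, 72–84% still point the right way.
- **The threshold guarantees at most one subject in most arms.** That describes a site of exactly five in blocks of 4. Larger sites and the pooled group hold more.

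On remedies, pooling to four per arm does not make site differences precise. The SE becomes SD × √(2/4) = 1.41–2.12 mmHg, with 8–17% still favouring placebo. Random site-by-treatment variances are also weakly identified at about 1.7 subjects per cell.

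**Conclusion.** The concern holds in limited form. A pooling threshold on total site size does not protect a full treatment-by-site interaction across four arms. The site-averaged difference for a given concentration is at substantial risk of being non-estimable: 28–63% with blocks of 4, 58–78% with blocks of 8, and nearly always without blocking, all with 5% missing. It is near 0% with blocks of 4 and complete data. Site-level differences are usually estimable under blocking, but too imprecise to show either consistency or inconsistency. The plan does not say which of the two the site table will show.

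The first result depends on the unstated block size, the missingness and the spread of site sizes; the second on a residual SD of 2.0–3.0 mmHg and 1.5–2 subjects per cell. Severity is minor.

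**What to change.** In SAP 13.3, replace the threshold of five subjects in total with a per-arm minimum. Combine small sites by a rule fixed before unmasking so that every pooled site has several observed subjects in each arm, for example at least 4 per arm. That is 16 per pooled site, so at most 208/16 = 13 levels. State whether Table 14.2.6.1 reports site-level or site-averaged differences, and what is done if a cell is still empty.

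Alternatively, estimate the treatment difference from a model with site as a main effect only, or with random site and site-by-treatment effects, and report no site-level p-values.

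The cost is SAP wording and one program. Individual small sites are no longer examined separately. SAP 13.3 and Section 20 describe some analyses as already done; if this table has been produced, the change must be labelled post hoc.

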15.1 Adverse Events

An AE is defined as any untoward medical occurrence associated with the use of a drug in humans, whether or not the event is considered drug-related. All AEs occurring during the study, regardless of the assumption of causal relationship, must be documented on the respective CRF. AEs should be

documented from the time the subject receives the first dose of study drug until 30 days after the last dose of study drug.

Treatment-emergent adverse events (TEAEs) are defined as any event that occurs or worsens on or after the day that randomized study treatment is initiated, and by study completion date.

Adverse events are coded using the MedDRA/J, Version 21.1. An overall summary will be presented to report the number of events and incidents of subjects having at least one event in the following categories:

- TEAEs
- Ocular TEAEs
- Non-ocular TEAEs
- Serious TEAEs
- Treatment-related TEAEs (reported as possibly related or related to the study drug)
- Treatment-related serious TEAEs
- TEAEs by maximum severity
- TEAEs leading to study drug discontinuation
- TEAEs resulting in death

Separate summaries will be provided for the number and percentage of TEAEs by SOC and PT for the following categories as well as the p-values for comparing the incidence between each netarsudil (0.01%, 0.02%, and 0.04%) group and placebo:

- Ocular TEAEs
- Non-ocular TEAEs
- Serious TEAEs
- Treatment-related TEAEs (reported as possibly related or related to the study drug)

If a subject reports the same PT multiple times within the same SOC, that PT will only be reported once within that SOC. As with the PT, if a subject reports multiple conditions within the same SOC, that SOC will only be reported once. In the summary, SOC will be listed in ascending alphabetical order; PTs will be listed in order of descending frequency within each SOC.

Treatment-emergent AEs will also be summarized by SOC, PT, and maximum severity. If a subject experiences more than one AE within SOC or PT, that subject will be counted only once for that event under the maximum severity.

All AEs will be presented in a subject listing. In addition, all serious AEs and AEs leading to study drug discontinuation will be listed separately.

15.2 Best Corrected Visual Acuity

Best corrected visual acuity will be measured using Landolt-C chart or its equivalents at Visit 1, Visit 2, Visit 3.0, Visit 4.0, Visit 5.0, and Visit 6.0.

Best corrected visual acuity data for both the study eye and the fellow eye will be summarized for each visit and for change from baseline to each post-treatment visit using the continuous summary statistics.

A subject listing of the BCVA results will be produced.

15.3 Biomicroscopy Examination

Biomicroscopy examination of the lids, conjunctiva, cornea, anterior chamber, lens, and iris/pupil will be performed for both eyes of subjects at every study visit.

The results will be summarized using counts and percentages for each treatment group at each visit for study eye and fellow eye separately. Percentages will be based on the number of subjects in each treatment group with non-missing values.

A summary table of the number and percentage of subjects with at least one severity grade increase from baseline will be presented by region, finding, visit, and eye (study eye and fellow eye). Another summary table will be presented for the number and percentage of subjects with biomicroscopy finding judged to be clinically significant by the Investigator by region, finding, visit time point, and eye (study eye and fellow eye). Fisher's exact tests will be used to compare incidence between treatment groups in both tables. Note: iris/pupil will not be analyzed in the table.

Additionally, Conjunctival hyperemia will also be summarized using continuous summary statistics including change from baseline and change from Visit 1. Two-sample t-tests as well as Wilcoxon rank sum tests will be used to test the difference between treatment groups.

A subject listing of the biomicroscopy parameter results will be produced. A separate listing will be generated for subjects with a criterion change, defined as a +1 unit increase from baseline.

15.4 Dilated Ophthalmoscopy

A dilated funduscopic examination including evaluation of the retina, vitreous, macula, choroid, optic nerve, and vertical cup/disc ratio will be performed at Visit 1 and Visit 6.2.

The results including retina, vitreous, macula, choroid, and optic nerve will be summarized using counts and percentages for each treatment group at each visit for study eye and fellow eye. Percentages will be based on the number of subjects in each treatment group with non-missing values. A shift table of ophthalmoscopy results from baseline will also be presented by treatment group for study eye and fellow eye separately.

The vertical cup-to-disc ratio will be summarized for study eye and fellow eye at each visit and change from baseline to each visit using continuous summary statistics.

Subject listings of the dilated ophthalmoscopy results (one listing for retina, vitreous, macula, choroid, and optic nerve, one listing for vertical cup-to-disc ratio) will be produced. A separate listing will be created for those subjects with a criterion change, defined as a change from "Normal" to "Abnormal" or a change from "Abnormal – Not Clinically Significant" to "Abnormal – Clinically Significant". Additionally, a listing of subjects with increases of ≥ 0.2 from the screening vertical cup-to-disc ratio will be created.

15.5 Vital Signs

Vital signs, including heart rate and blood pressure, will be measured at Visit 1, Visit 2, Visit 3.0, Visit 4.0, Visit 5.0, and Visit 6.0.

Vital signs will be summarized for each visit and for change from baseline to each post-treatment visit using the continuous summary statistics.

A subject listing of the vital signs results will also be produced.

15.6 Clinical Laboratory Data

Clinical laboratory data including clinical chemistry, hematology, and urinalysis will be collected at Visit 1 or Visit 2 (if not performed at Visit 1), and Visit 6.0.

Quantitative clinical laboratory results will be summarized for each visit and for change from baseline to Visit 6.0 using continuous summary statistics. Qualitative clinical laboratory results will be summarized using discrete summary statistics. Shifts from baseline to Visit 6.0 will also be presented using discrete summary statistics. Additionally, number and percentage of subjects with any abnormal values in clinical chemistry and hematology will be summarized by treatment group.

Clinical laboratory results, including clinical chemistry, hematology, and urinalysis/urine microscopic, will be presented in data listings. Abnormal results, those above or below the normal range, will be flagged with "H" (high), "HP" (high panic), "L" (low), "LP" (low panic), or "AB" (abnormal) based on the laboratory ranges provided by the lab and included in the listings.

16. Safety Analyses – Observational Period

Cornea verticillata safety population will be used in the analyses for observational period.

Listings of subject disposition, demographics and baseline characteristics, and AEs (all AEs, serious AEs, AEs resulting in study drug discontinuation) will be produced. Summary of subject disposition, demographics and baseline characteristics, and TEAEs will be summarized similarly to those for treatment period.

16.1 Visual Function Questionnaire

The subjects who develop cornea verticillata will undergo VFQ-25 at OBS Visit 1 (when cornea verticillata is diagnosed) and the final visit. The scores and the score changes from OBS Visit 1 will be summarized using the continuous summary statistics by treatment group.

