In subjects who develop cornea verticillata, CS and BCVA will be summarized at the eye level (that is, if a subject has a cornea verticillata in both eyes, then both eyes will be included) for the initial assessments and for follow-up visits as well as change from the initial assessment (for visual acuity, change from baseline, as defined for the Treatment Period will also be completed), by treatment group and by whether or not the cornea verticillata deposit event is ongoing at given visit. The VFQ-25 scores will be summarized similarly at the subject level.

Resolution of cornea verticillata is defined as a cornea verticillata deposit grade of zero. Stabilization is defined as no worsening of the cornea verticillata grading for a minimum of one year from the commencement of dosing. The time to cornea verticillata resolution/stabilization will be evaluated in days related to start date of cornea verticillata at the eye level. Kaplan-Meier methods will be used to estimate median time to cornea verticillata resolution/stabilization, as well as the 25th and 75th percentiles by treatment group and overall netarsudil treated subjects. Associated 95% confidence interval will also be estimated. Kaplan-Meier curves will also be presented by treatment group and overall netarsudil treated subjects.

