16.2 Best Corrected Visual Acuity

Best Corrected Visual Acuity will be taken at all visits during the observational period. Best correct visual acuity collected during the observation period will be summarized similarly to that of treatment period.

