16.3 Contrast Sensitivity Testing

The CS testing will undergo at OBS Visit 1 (when cornea verticillata is diagnosed) and the final visit. The CS results will be summarized at eye level using discrete summary statistics for each spatial frequency by treatment group, and by whether or not the corneal verticillata deposit event is ongoing at given visit. The numeric part of the CS results will be summarized at eye level using the continuous summary statistics.

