16.4 Cornea Verticillata Grading

Subjects who are diagnosed with cornea verticillata by slit lamp examination will undergo grading of the corneal deposits using a published grading scale for amiodarone-induced cornea verticillata. The corneal deposits will be graded at all visits during the observational period. The scores and the score changes from Visit 1 will be summarized at eye level using continuous summary statistics by treatment group, and by whether or not the cornea verticillata deposit event is ongoing at given visit.

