14.3.6.9	Summary of Urinalysis and Urine Microscopic Categorical Values by Treatment Group and Visit	Safety Population
14.4.1	Subject Disposition Cornea Verticillata	Safety Population

14.4.2	Demographics and Baseline Characteristics by Treatment Group Cornea Verticillata	Safety Population
14.4.3.1	Number and Percentage of Subjects with Ocular Treatment-Emergent Adverse Events by Treatment Group, System Organ Class, and Preferred Term Cornea Verticillata	Safety Population
14.4.3.2	Number and Percentage of Subjects with Non-Ocular Treatment-Emergent Adverse Events by Treatment Group, System Organ Class, and Preferred Term Cornea Verticillata	Safety Population
14.4.4	Mean and Mean Change from Visit 1 in Visual Function Questionnaire (VFQ-25) Results by Treatment Group Cornea Verticillata	Safety Population
14.4.5.1	Mean, Mean Change from Baseline, and Mean Change from OBS Visit 1 in Study Eye Best Corrected Visual Acuity Results by Treatment Group Cornea Verticillata	Safety Population
14.4.5.2	Mean, Mean Change from Baseline, and Mean Change from OBS Visit 1 in Fellow Eye Best Corrected Visual Acuity Results by Treatment Group Cornea Verticillata	Safety Population
14.4.6.1	Summary of Contrast Sensitivity Testing in Study Eye by Treatment Group, and Visit Cornea Verticillata	Safety Population
14.4.6.2	Summary of Contrast Sensitivity Testing in Fellow Eye by Treatment Group, and Visit Cornea Verticillata	Safety Population
14.4.7.1	Mean and Mean Change from OBS Visit 1 in Study Eye Cornea Verticillata Grading by Treatment Group Cornea Verticillata	Safety Population
14.4.7.2	Mean and Mean Change from OBS Visit 1 in Fellow Eye Cornea Verticillata Grading by Treatment Group Cornea Verticillata	Safety Population
14.4.7.3	Time to Cornea Verticillata Resolution/Stabilization in Study Eye by Treatment Group and Overall Netarsudil-Treated Subjects Cornea Verticillata	Safety Population
14.4.7.4	Time to Cornea Verticillata Resolution/Stabilization in Fellow Eye by Treatment Group and Overall Netarsudil-Treated Subjects Cornea Verticillata	Safety Population

22. Listings

Listing Number	Title
16.1.7	Randomization Schedule
16.2.1.1	Subject Disposition
16.2.1.2	Subject Who Prematurely Discontinued
16.2.1.3	Subject Disposition for Screen Failure Subjects

16.2.2	Protocol Deviations
16.2.3.1	Analysis Populations Information
16.2.3.2	Inclusion Criteria Not Met/Exclusion Criteria Met for Screen Failures
16.2.4.1	Demographics and Baseline Characteristics

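### For subjects with cornea verticillata, no planned summary shows how VFQ-25 or contrast sensitivity changed from the pre-dose Visit 3 values

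*SAP*

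**What the plan says.** Protocol 6.12 and 6.13 schedule VFQ-25 and CS for all subjects at Visit 3. Exclusion 9 in protocol 4.3 keeps out anyone with corneal deposits, so these values precede both dosing and deposits. Protocol 7.4.1 and 7.4.4 repeat both measures in verticillata subjects at OBS Visit 1 and at the final visit. SAP 8.3 defines baseline for these variables as the last pre-dose value, which is Visit 3.

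For the observational period, protocol 9.7.2 (Amendment 1) plans CS and BCVA summaries "for the initial assessments and for follow-up visits as well as change from the initial assessment". It adds a second reference point for one measure only: "for visual acuity, change from baseline, as defined for the Treatment Period will also be completed". For the questionnaire it says "The VFQ-25 scores will be summarized similarly at the subject level".

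The SAP handles the measures as follows:

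- **VFQ-25 (16.1):** "The scores and the score changes from OBS Visit 1 will be summarized using the continuous summary statistics by treatment group". Table 14.4.4 in Section 21 is titled "Mean and Mean Change from Visit 1 in Visual Function Questionnaire (VFQ-25) Results by Treatment Group".
- **CS (16.3):** discrete summaries by spatial frequency, and "The numeric part of the CS results will be summarized at eye level using the continuous summary statistics". Neither this section nor the titles of Tables 14.4.6.1-2 name a change score.
- **BCVA (16.2):** "Best correct visual acuity collected during the observation period will be summarized similarly to that of treatment period". SAP 15.2 includes change from baseline, and the titles of Tables 14.4.5.1-2 name change from baseline and from OBS Visit 1.
- **Grading (16.4):** "The scores and the score changes from Visit 1 will be summarized at eye level using continuous summary statistics by treatment group". The titles of Tables 14.4.7.1-2 say OBS Visit 1.

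**The concern.** Protocol 3.2 gives the reason for following these subjects: to learn how cornea verticillata affects visual function, and whether it resolves, in a Japanese population. The first half of that question asks what happened to vision between the pre-dose state and the time with deposits, and whether any loss remained. OBS Visit 1 is the visit at which deposits are detected and study drug is stopped. A change measured from there starts after any loss that came with the deposits.

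The wording of a VFQ-25 result is at stake. A mean change near zero could be read as no effect on visual function when it means only that nothing moved after detection. A positive change could be read as improvement when it is recovery. For CS, no change of any kind is named in the SAP. The pre-dose values that would settle the matter are collected in every subject.

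**Working it through.** The plan states no figure to reproduce. The check sets the named change scores side by side, followed by simple arithmetic.

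**Named change scores, observational period**

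| Measure | From pre-dose baseline | From OBS Visit 1 |
|---|---|---|
| BCVA | Yes (Tables 14.4.5.1-2) | Yes (same tables) |
| VFQ-25 | No | Yes (SAP 16.1) |
| CS | No | Protocol Amendment 1 only; not in SAP 16.3 or Tables 14.4.6.1-2 |

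The protocol's initial assessment cannot be read as Visit 3. Protocol 9.7.1 speaks of the initial visit of the observational period, and 9.7.2 adds the treatment-period baseline separately, for visual acuity alone.

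**What the planned VFQ-25 change measures.** Let V, O and F be a subject's scores at Visit 3, OBS Visit 1 and the final visit.

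- Planned change: F − O
- Change at detection: O − V
- Residual change: F − V = (F − O) + (O − V)

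V does not enter the planned change. Hypothetical scores, where higher is better:

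| V / O / F | Planned, F − O | At detection, O − V | Residual, F − V |
|---|---|---|---|
| 90 / 84 / 84 | 0 | −6 | −6 |
| 90 / 84 / 87 | +3 | −6 | −3 |
| 90 / 84 / 90 | +6 | −6 | 0 |
| 84 / 84 / 90 | +6 | 0 | +6 |

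The last two rows give the same planned change, yet one subject lost 6 points and recovered while the other never lost any.

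**Where the pre-dose values appear**

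- Tables 14.1.3.4-6 summarise Visit 3 for the whole safety population, so their means are not the verticillata subjects' own baseline.
- SAP 10.2 says pretreatment variables accompany post-treatment ones in relevant summaries and listings. This may put Visit 3 means into the 14.4 tables, but no paired change is named.
- Listings 16.2.13 and 16.2.14 (VFQ-25 and CS), with 16.3.4 and 16.3.6 (the same measures, observational period), give the subject-level values. SAP 8.4 lists all study data for all randomized subjects. Paired changes, with their SD and range, can be computed from these.

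**How many subjects.** The verticillata rate in this 28-day trial is unknown. The three active arms hold 3 × 52 = 156 subjects. Illustrative rates:

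- 1% (arbitrary low value): 0.01 × 156 = 1.6, or 0.5 per arm
- 76/454 = 16.7% (earlier once-daily rate, protocol 1.1): 26.1, or 8.7 per arm
- 64/253 = 25.3% (earlier twice-daily rate, a regimen not used here): 39.5, or 13.2 per arm

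The two earlier rates come from studies with first detection between 2 and 13 weeks, so they may not carry over to 28 days.

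**The case against.** The strongest reply is that a reader might infer the pre-dose comparison cannot be made, and that would be wrong. The planned listings hold each subject's Visit 3, OBS Visit 1 and final values, and at small numbers the paired changes are easily worked out. This stands in full: the gap is an unplanned summary.

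Second, the VFQ-25 reference point is a stated choice. A reader might infer that SAP 16.1 conflicts with the protocol. It does not: protocol 9.7.2 limits the extra baseline comparison to visual acuity, and the SAP follows it.

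Third, the pre-dose question is partly answered. BCVA change from baseline is planned, and Listing 16.2.8.2 shows subjects who lost three or more lines. In subjects whose deposits resolve, OBS Visit 1 to final compares eyes with and without deposits, which also bears on visual impact. This stands, but it cannot show a loss that persists, and BCVA does not stand in for patient-reported function or contrast.

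Fourth, a reader might infer that the SAP silently dropped a CS change score planned in the protocol. The documents do not establish this. The SAP implements Amendment 2, dated 01 MAR 2019; the protocol available is Amendment 1. SAP Section 18 lists departures from Amendment 2, so its silence proves nothing about Amendment 1 text, and SAP Section 1 says its methods supersede the protocol's.

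Fifth, a reader might take Visit 1 in Table 14.4.4 and SAP 16.4 to mean Screening. Neither VFQ-25 nor verticillata grading is scheduled there, so only OBS Visit 1 is possible. The label is a clerical slip and leads to no wrong calculation.

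Finally, change from Visit 3 is itself imperfect. Subjects without verticillata do not repeat either measure, so there is no comparator.

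**Conclusion.** The point holds as a modest, descriptive one. For VFQ-25 and CS in verticillata subjects, no planned summary names the change from the pre-dose state, while BCVA has one. The planned VFQ-25 change would show a persisting loss as zero and a recovered loss as an improvement, so by itself it does not answer the visual-function question in protocol 3.2.

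The size is limited. No data are lost, no inference is planned on these measures, and the primary efficacy result is untouched. The score examples are hypothetical and the subject counts rest on assumed rates; neither predicts what the trial will show. A change from Visit 3 would not isolate the effect of deposits either. It would describe how far these subjects were from where they started. Confidence is high for what the SAP names and does not name. Whether the CS omission departs from the governing protocol stays open until Amendment 2 is checked.

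**What to change.** 1. In SAP 16.1 and 16.3 and in Tables 14.4.4 and 14.4.6.1-2, add paired change from the Visit 3 baseline (SAP 8.3) to OBS Visit 1 and to the final visit, by treatment group. Do this at subject level for VFQ-25, and at eye level per spatial frequency for the numeric part of CS. Because the SAP refers to a numeric part of the CS result, state which results enter the change. Keep change from OBS Visit 1 for VFQ-25.
2. Add a footnote: there is no comparator; the change mixes deposits with other drug effects, repeat testing and any IOP-lowering treatment used by the final visit (permitted by protocol 6.20.3); numbers may be very small.
3. Check Amendment 2 for CS change from the initial assessment. If it is still planned there, include it or list its removal in SAP Section 18.
4. Correct Visit 1 to OBS Visit 1 in the title of Table 14.4.4 and in SAP 16.4.

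The cost is a few descriptive columns in three tables and two label corrections, using data already collected. SAP 13.3 describes some post-hoc work as already done, so the analyses may be complete. In that case, report the change from Visit 3 as a supplementary analysis identified in the clinical study report, as SAP Section 1 allows.
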